# **Study Protocol**

**Official Title:**

**The Effects of Virtual Reality with Debriefing on Patients with Chronic Pain**

**ClinicalTrials.gov ID (NCT number):**

**NCT04236804**

**Protocol Date:**

**2024-12-20**

## Scientific Background

Chronic musculoskeletal pain, defined as persistent or recurrent pain lasting more than three months, is a disabling condition with significant physiological and psychosocial implications. Unlike acute pain, chronic pain serves no adaptive purpose, as it often persists after the original precipitating event (e.g., fracture, sprain, trauma) has resolved.

Immersive Virtual Reality (IVR) has shown potential as a treatment for acute pain, but its use for chronic pain remains underexplored. IVR enables individuals to immerse themselves in a three-dimensional environment, promoting normal movement patterns by distracting them from their pain. This study examines the effects of IVR combined with occupational therapy (OT) to determine whether it reduces chronic pain and associated symptoms more effectively than OT alone.

## Study Objectives

- Primary Objective: To evaluate changes in Morphine Milligram Equivalent (MME) use from baseline to three months in patients receiving OT with or without IVR.
- Secondary Objectives:
  - To assess changes in chronic pain intensity using the Numeric Pain Rating Scale.
  - To evaluate self-efficacy, fear of movement, and functional participation using validated scales, including the Pain Self-Efficacy Questionnaire, the Tampa Scale of Kinesiophobia, and the Goal Attainment Scale.
  - To assess changes in patient-reported outcomes such as sleep disturbance, physical function, and emotional well-being using PROMIS measures.

## Study Design & Methods

- Study Type: Interventional
- Allocation: Randomized
- Interventional Model: Parallel Assignment
- Masking: None (Open Label)
- Primary Purpose: Treatment

### Arms and Interventions:

1. Active Comparator: Occupational Therapy (OT)
  - Participants receive six 1-hour outpatient OT sessions tailored to chronic pain management, including education, exercises, stress management, and daily activity planning.
2. Experimental: Occupational Therapy + Virtual Reality (OT+VR)
  - Participants receive a combination of OT and 10–30 minutes of IVR during each session. IVR sessions include interactive exercises and games, followed by therapist-led debriefing.

### Measurements:

- Participants complete surveys before and after each therapy session.
- Additional bi-weekly online surveys are administered for the study duration.

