**Exclusion Criteria:**

- History of seizure disorders or recent VR intervention.
- Sensory insensitivity or contagious facial disorders incompatible with VR headset use.
- Insufficient cognitive ability or physical coordination for IVR use.

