**Secondary Analysis:**

- Changes in PROMIS measures (e.g., pain intensity, fatigue, and depression) will be analyzed using similar methods. Adjustments will be made for baseline values in secondary outcomes using linear regression.

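### No harm or tolerability outcome is pre-specified for the IVR arm, so the plan supports no tolerability comparison and cannot separate poor tolerability from lack of efficacy

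*Combined protocol and SAP*

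**What the plan says.** Apart from the primary outcome, change in MME, Study Objectives lists three groups of outcomes: "To assess changes in chronic pain intensity using the Numeric Pain Rating Scale"; "To evaluate self-efficacy, fear of movement, and functional participation using validated scales"; and "To assess changes in patient-reported outcomes such as sleep disturbance, physical function, and emotional well-being using PROMIS measures". Secondary Analysis adds "Changes in PROMIS measures (e.g., pain intensity, fatigue, and depression) will be analyzed using similar methods".

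Under Arms and Interventions, the experimental arm is described as follows: "Participants receive a combination of OT and 10–30 minutes of IVR during each session". The IVR consists of interactive exercises and games, with a therapist debriefing afterwards.

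Under Measurements, "Participants complete surveys before and after each therapy session", and there are further online surveys every two weeks. The content of neither survey is given.

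The Exclusion Criteria rule out people with a seizure history, with reduced sensation, with contagious facial conditions that prevent headset use, and with "Insufficient cognitive ability or physical coordination for IVR use".

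Subgroup and Sensitivity Analyses names treatment adherence as a subgroup variable, without a definition.

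**The concern.** The randomised contrast is the addition of IVR to OT. A report on that addition should be able to say what it cost patients as well as what it gained them, and nothing pre-specified in the plan supplies the first part.

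Interpretation is also at stake. If nausea, dizziness or a pain increase leads to shorter IVR or to dropout, the arms will look more alike. Without symptom or exposure data, that result would be read as lack of efficacy. Handling Missing Data also assumes that data are missing at random. If unrecorded symptoms drive dropout, that assumption is harder to defend and cannot be examined.

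Data on harm and exposure that were never collected cannot be supplied at the analysis stage. The gap therefore concerns what is measured, not only how the plan is worded.

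**Working it through.** The plan gives no figure on this point to reproduce. The check is an inventory of outcomes, followed by a calculation of what added data could show.

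**1. Inventory of named outcomes**

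| Outcome | Where named | Harm or tolerability outcome? |
|---|---|---|
| MME | Study Objectives; Primary Analysis | No |
| Numeric Pain Rating Scale | Study Objectives | No |
| Pain Self-Efficacy Questionnaire, Tampa Scale of Kinesiophobia, Goal Attainment Scale | Study Objectives | No |
| PROMIS domains | Study Objectives; Primary and Secondary Analysis | No |

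Harm or tolerability outcomes: 0. Nothing in Statistical Considerations or the paragraphs that follow it tabulates adverse events, side effects or discontinuation because of VR.

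**2. Other places where a signal could appear**

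- Session and bi-weekly surveys: content not stated.
- Treatment adherence: an undefined subgroup variable, with no reason for non-adherence attached.

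**3. Exposure**

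Six sessions are stated for the OT arm and assumed here for OT+VR. Planned IVR per patient then runs from 6 × 10 = 60 to 6 × 30 = 180 minutes, a threefold range. No record of minutes delivered is stated.

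**4. What added data could show**

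Inputs: n = 20 in total (Challenges Due to Small Sample Size). The allocation ratio is not stated, so 10 VR patients are assumed, with a range of 8 to 12.

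Exact 95% upper limit with no patient affected: one-sided 1 − 0.05^(1/n), two-sided 1 − 0.025^(1/n).

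| VR patients | One-sided | Two-sided |
|---|---|---|
| 8 | 31.2% | 36.9% |
| 10 | 25.9% | 30.8% |
| 12 | 22.1% | 26.5% |

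With 2 of 10 affected, the exact two-sided 95% interval is 2.5% to 55.6%.

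Chance of seeing at least one affected patient among 10, 1 − (1 − p)^10:

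- true rate 5%: 1 − 0.95^10 = 40%
- true rate 10%: 1 − 0.90^10 = 65%
- true rate 20%: 1 − 0.80^10 = 89%

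A common problem would probably be seen, but its rate would be known only roughly.

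**The case against.** Several stronger readings are tempting, and the documents do not support them.

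- *Nothing on tolerability is collected, so no statement could ever be made.* Survey content is not given, and a symptom item may already be there. What can be shown is that no harm outcome or analysis is pre-specified.
- *The endpoints can only register benefit.* Pain, fear of movement and fatigue can all worsen. A pain rating may already be taken on both sides of each session, which would capture a post-session increase. The plan does not say which scale is in which survey. A mean change, however, does not count patients with a flare, and none of the named scales is a measure of nausea, dizziness or falls.
- *The exclusions prove that the sponsor sees VR as hazardous.* This is uneven. The seizure criterion, and arguably reduced sensation, point to participant risk. Facial conditions may be a matter of headset hygiene, the coordination criterion may be about operating the system, and recent VR use need not be a hazard criterion at all. The point stands without this inference.
- *Sixty VR sessions (10 patients × 6) with no event would give a tight limit.* The figure 1 − 0.05^(1/60) = 4.9% treats repeated sessions in the same people as independent, and should not be used.

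Two further objections have weight. The plan calls its findings exploratory, warns of Type II error and makes no safety claim, so there is no false statement to withdraw. And with about 10 VR patients, added items yield only wide intervals. Both bear on how much can be claimed. Neither is a reason to leave harm and exposure unmeasured in a study of adding a device-based component.

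Timing is open. Parts of the statistical text read as if written late in the study, and enrolment status is not stated. If sessions are finished, items and logs cannot be added.

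**Conclusion.** The point holds in this form: no harm or tolerability outcome or analysis is pre-specified for the IVR arm, and the session survey has no stated harm content. The plan as written supports no tolerability comparison, and it cannot tell poor tolerability or shortened exposure from lack of efficacy. Adherence does not fill the gap.

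This is a cheap improvement, not a flaw that invalidates the efficacy analysis. The benefit is descriptive, with the limits shown above. They rest on an assumed 8 to 12 VR patients, and the exposure range rests on six sessions in that arm. The finding does not assert that tolerability information is absent from the surveys, nor that IVR is poorly tolerated. The documents are silent on both.

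**What to change.** 1. State what the post-session survey contains. Unless already included, add brief yes/no items in both arms for nausea, dizziness, headache or eye strain, and fall or near-fall.
2. If a pain rating is taken before and after each session, use it to identify a post-session increase. Otherwise add one item.
3. Have the therapist log IVR minutes delivered and any early stop with its reason.
4. In Secondary Analysis, add a descriptive by-arm table of patients affected, with exact confidence limits. Count patients, and do not use a per-session limit that assumes independence.
5. If data collection is already complete, tabulate whatever session records exist, state that harms were not systematically collected, and draw no conclusion on tolerability.

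Cost: about a minute more per session, one log entry and one table. The change concerns measurement and reporting only, and leaves treatment delivery and the efficacy analysis as they are.

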## Eligibility Criteria

**Inclusion Criteria:**

- Adults aged 18 years or older.
- Referred for chronic pain OT at UPMC Centers for Rehab Services.

**Exclusion Criteria:**

- History of seizure disorders or recent VR intervention.
- Sensory insensitivity or contagious facial disorders incompatible with VR headset use.
- Insufficient cognitive ability or physical coordination for IVR use.

## **Statistical Considerations**

This study was designed to evaluate the effects of occupational therapy with or without immersive virtual reality on MME and patient-reported outcomes over an 8-week period. Following consultation with study clinicians, the primary outcome was revised to focus on patient-reported changes in MME from baseline to 8 weeks, ensuring alignment with the study's therapeutic goals.

**Primary Analysis:**

- Within-group changes in MME and PROMIS measures from baseline to 8 weeks will be analyzed using paired t-tests or Wilcoxon signed-rank tests (for non-normally distributed data).
- Between-group differences will be assessed using independent t-tests or Mann-Whitney U tests.

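### The Primary Analysis lists within-arm and between-arm tests without saying which decides the MME result, and it includes PROMIS, which is secondary elsewhere

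*Combined protocol and SAP*

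**What the plan says.** All sections cited are in the combined protocol and SAP.

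- **Outcome.** Statistical Considerations states that "the primary outcome was revised to focus on patient-reported changes in MME from baseline to 8 weeks". It names a variable and a time, but no contrast between arms.
- **Tests.** Primary Analysis has two bullets. The first reads "Within-group changes in MME and PROMIS measures from baseline to 8 weeks will be analyzed using paired t-tests or Wilcoxon signed-rank tests". The second reads "Between-group differences will be assessed using independent t-tests or Mann-Whitney U tests" and does not name an outcome. Neither is marked as decisive.
- **Adjustment.** Secondary Analysis says "Adjustments will be made for baseline values in secondary outcomes using linear regression", so regression is given only for secondary outcomes. Adjustment for Covariates mentions baseline MME, but only where judged appropriate.
- **PROMIS.** Under the secondary objectives: "To assess changes in patient-reported outcomes such as sleep disturbance, physical function, and emotional well-being using PROMIS measures". Under Secondary Analysis: "Changes in PROMIS measures (e.g., pain intensity, fatigue, and depression) will be analyzed using similar methods". It also stands beside MME in the first bullet of Primary Analysis.
- **Design.** The trial is randomised and open label, with "Interventional Model: Parallel Assignment". The comparator arm receives OT. In the experimental arm "Participants receive a combination of OT and" 10 to 30 minutes of VR at each session.

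**The concern.** A fall in MME within the OT+VR arm mixes the effect of OT, the passage of time, regression to the mean and any effect of VR. Only the comparison with the OT arm separates out VR. Yet the within-arm tests come first under the heading that should define the primary result, and the plan has no rule for the case where the two kinds of test disagree.

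The practical risk is a report in which MME falls significantly with OT+VR and not with OT alone, shown as a primary result and read as a benefit of VR. Two arms with the same true improvement will often give that picture at this sample size, because each arm's test has moderate power and chance decides which arm crosses 5%.

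The PROMIS point is smaller. One sentence gives PROMIS primary standing while two other sections make it secondary, so a favourable PROMIS result could be reported at either level.

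**Working it through.** **Inputs.** The documents give n=20 in total (Challenges Due to Small Sample Size). They give no allocation ratio, alpha, SD or effect size, so there is no stated figure to reproduce. Assumed here: a 10/10 split (8/12 and 12/8 as a range), two-sided 5%, normal change scores, no dropout, and the same true mean improvement δ in both arms, so that VR adds nothing. δ is in SDs of the change.

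**Step 1: power of one within-arm paired t-test.** The statistic follows a noncentral t with n−1 degrees of freedom and noncentrality δ√n. For n=10 and δ = 0.5, 0.7 and 1.0, power is 29.3%, 50.6% and 80.3%.

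**Step 2: only the OT+VR arm significant.** The arms are independent, so the probability is (power in OT+VR) × (1 − power in OT):

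- δ=0.5: 0.293 × 0.707 = 20.7%
- δ=0.7: 0.506 × 0.494 = 25.0%
- δ=1.0: 0.803 × 0.197 = 15.8%

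**Step 3: disagreement with the between-arm test.** This was found by simulation at 10/10: 200,000 trials for the t-tests, and 100,000 for exact Wilcoxon (W≤8) and Mann-Whitney (U≤23 or ≥77).

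| | δ=0.5 | δ=0.7 | δ=1.0 |
|---|---|---|---|
| OT+VR only, paired t, 10/10 | 20.7% | 25.0% | 15.8% |
| Same, OT+VR 8 and OT 12 | 15.0% | 16.1% | 8.0% |
| Same, OT+VR 12 and OT 8 | 27.1% | 35.9% | 28.2% |
| OT+VR only, and between-arm t-test not significant | 18.4% | 22.7% | 14.3% |
| OT+VR only, Wilcoxon | 20.2% | 25.1% | 16.7% |
| OT+VR only, Wilcoxon, and Mann-Whitney not significant | 18.3% | 23.2% | 15.4% |

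The between-arm t-test has a type I error of 4.9 to 5.0% and Mann-Whitney 4.4%, whatever the common improvement. With no change in either arm, OT+VR alone shows a significant improvement in 2.4% of trials.

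**Step 4: what a baseline-adjusted primary test would give.** Normal data, 10/10, 40,000 runs; half-widths are in SDs of MME.

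| Baseline/8-week correlation | 0.3 | 0.5 | 0.7 |
|---|---|---|---|
| Type I error, adjusted regression | 5.0% | 5.1% | 5.0% |
| Median 95% CI half-width, adjusted | 0.91 | 0.82 | 0.68 |
| Median 95% CI half-width, unadjusted change | 1.09 | 0.92 | 0.71 |

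A skewed illustration used lognormal baseline MME (log-SD 0.8 or 1.2), 0, 20 or 40% zeros that stay zero, and the same proportional fall in both arms. Type I error was 2.7 to 4.1% for the regression and 4.2 to 4.7% for Mann-Whitney on change.

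**The case against.** **The design already implies the between-arm test.** The trial is randomised with an active comparator, and the Scientific Background asks whether the combination does better than OT alone. This makes the between-arm reading the natural one. But that aim is worded for pain and symptoms, the MME objective can be read either way, and no sentence names the deciding test.

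**The findings are declared exploratory, and both tests would be reported.** The plan sets no success criterion, so a within-arm result does not formally meet one; it misleads only if the between-arm result is passed over. That lowers the stakes. It does not remove the need for one stated contrast in a trial that declares a primary outcome and a primary analysis.

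**The figures use a favourable range.** At a common improvement of 0.3 SD the pattern occurs in about 12% of trials. In a skewed illustration (30% or 50% median fall in users, exact Wilcoxon, 2,000 runs) it occurred in about 12 to 24% with 0 to 40% zeros, but in only about 4 to 10% with 60% zeros. Eligibility does not require opioid use and the documents do not give the proportion of non-users. This limit stands.

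**Regression goes further than the gap requires.** Naming the planned between-arm test would by itself cure the ambiguity; that is true. The case for regression is the narrower interval for normal data and the plan's own mention of baseline adjustment. Its cost is some conservatism with skewed MME. In a separate skewed, zero-heavy illustration its type I error was 3.5 to 4.1%, and its power exceeded that of Mann-Whitney on change (75% against 53% with no zeros, 47% against 19% with 40% zeros). Those powers depend on an assumed effect, so only their order is useful here.

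**Conclusion.** The concern holds. The plan has a primary outcome but no deciding contrast, and the tests it lists first cannot answer the question about VR. If both arms truly improve by 0.5 to 1.0 SD of the change and VR adds nothing, significance in the OT+VR arm alone occurs in 16 to 25% of trials at 10/10 (8 to 36% over splits 8/12 to 12/8). In 14 to 23% at 10/10 it contradicts the between-arm t-test listed beside it. Naming the between-arm test as decisive holds that error at about 5%.

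The size rests on an assumed split and alpha, on normal changes and on improvement in both arms; it shrinks if changes are small or most participants use no opioids. The gap in the text does not depend on these assumptions. The placement of PROMIS is an inconsistency of status and a minor one. Because the trial is exploratory, this should be fixed, but it does not invalidate the design.

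**What to change.** In Primary Analysis:

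1. Name one primary test: the between-arm difference in 8-week MME, from a linear regression on arm and baseline MME, with a 95% confidence interval. State the covariates there, since Adjustment for Covariates leaves the choice open.
2. Keep Mann-Whitney on change in MME as a sensitivity analysis for skewed or zero-heavy data.
3. Label within-arm changes descriptive and not evidence of a VR effect.
4. Remove PROMIS from this section, so that it is analysed once, under Secondary Analysis. This corrects its status; it does not reduce the number of PROMIS tests.

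If a new model is unwelcome, naming the planned between-arm test on MME change as decisive would still close the main gap.

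**Cost.** No new data are needed: MME at baseline and 8 weeks is already in the analysis plan. The primary objective still gives three months, a separate conflict that must be reconciled for the 8-week test to stand. Within-arm p-values lose primary standing. Regression becomes a new primary model, so the change should be recorded and dated relative to data access. The interval will be wide at n=20: about ±0.8 SD of MME at a correlation of 0.5 (0.7 to 0.9 for correlations from 0.7 down to 0.3), against about ±0.9 (0.7 to 1.1) unadjusted.

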**Handling Missing Data:**

- Missing data will be addressed using multiple imputation under the assumption that data are missing at random. Sensitivity analyses will compare results from imputed datasets with complete-case analyses.

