**Adjustment for Covariates:**

- Analyses will adjust for baseline MME, PROMIS scores, and demographic factors (age, gender) where appropriate.

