**Subgroup and Sensitivity Analyses:**

- Subgroup analyses will examine treatment adherence and baseline PROMIS scores. Sensitivity analyses will explore the impact of different imputation methods for missing data.

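### The plan does not settle whether the primary between-arm MME comparison adjusts for baseline MME, or which result leads; this costs precision and leaves a modest choice open

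*Combined protocol and SAP*

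**What the plan says.** All references are to the combined protocol and SAP.

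- **Statistical Considerations** sets the outcome: "the primary outcome was revised to focus on patient-reported changes in MME from baseline to 8 weeks".
- **Primary Analysis**, first bullet: "Within-group changes in MME and PROMIS measures from baseline to 8 weeks will be analyzed using paired t-tests or Wilcoxon signed-rank tests", the second test being for non-normal data. Second bullet: "Between-group differences will be assessed using independent t-tests or Mann-Whitney U tests". The second bullet does not name the quantity compared; read with the outcome definition, it is presumably the change in MME.
- **Secondary Analysis**: "Adjustments will be made for baseline values in secondary outcomes using linear regression".
- **Adjustment for Covariates**: "Analyses will adjust for baseline MME, PROMIS scores, and demographic factors (age, gender) where appropriate". No analysis, model or rule for deciding what is appropriate is given.
- **Handling Missing Data**: "Sensitivity analyses will compare results from imputed datasets with complete-case analyses". **Subgroup and Sensitivity Analyses**: "Sensitivity analyses will explore the impact of different imputation methods for missing data". Both concern missing data, and neither ranks an adjusted MME result against an unadjusted one.

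**The concern.** Neither a t-test nor a Mann-Whitney test can carry a covariate, and baseline regression is placed with the secondary outcomes. The natural reading is therefore an unadjusted primary test. The covariate section unsettles that reading. MME is the primary outcome, so listing baseline MME suggests that an adjusted MME analysis was contemplated. Two competent statisticians could follow the plan faithfully and report different primary results: a t-test on change, or a regression with one or several covariates.

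Two things are at stake. The first is precision: baseline MME must be collected anyway to compute change, and using it as a covariate usually narrows the interval, which matters with 20 participants. The second is the freedom to choose the lead result after seeing the data, in a trial that Study Design & Methods describes as open label.

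**Working it through.** The plan gives no figure to reproduce. The total of 20 comes from Challenges Due to Small Sample Size. The following are assumptions, not in the documents: 10 per arm, two-sided 5% level, equal SDs at both times, and baseline to 8-week correlation ρ from 0.3 to 0.9.

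**1. Precision, normal data.** In SD units, the change score has variance 2(1 − ρ) and the ANCOVA residual has variance 1 − ρ². Their ratio is (1 + ρ)/2. Allowing for chance imbalance in one covariate (factor 17/16) and the lost degree of freedom:

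CI width ratio, ANCOVA to change score = √[(1 + ρ)/2 × 17/16] × t(17)/t(18)

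| ρ | (1 + ρ)/2 | CI ratio | ANCOVA interval |
|---|---|---|---|
| 0.3 | 0.65 | 0.835 | about 17% narrower |
| 0.5 | 0.75 | 0.896 | about 10% narrower |
| 0.7 | 0.85 | 0.954 | about 5% narrower |
| 0.8 | 0.90 | 0.982 | about 2% narrower |
| 0.9 | 0.95 | 1.009 | about 1% wider |

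The ratio equals 1 at ρ = 0.867. For a true difference of 1 SD at ρ = 0.3, simulated power rises from about 44% to about 59%.

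**2. Chance imbalance.** The baseline gap between arms has SD √(2/10) = 0.447, so a gap above 0.5 SD has probability P(|z| > 0.5/0.447) = 26%. Such a gap shifts the expected change-score difference by (1 − ρ) × 0.5 SD. Against a standard error of √[2(1 − ρ) × 2/10], the shift is 0.66 SE at ρ = 0.3 and 0.25 SE at ρ = 0.9, which is smaller than sampling noise.

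**3. Open choice to adjust or not.** In 20,000 simulated null normal-data trials per ρ, the t-test on change and baseline ANCOVA each rejected in about 5%. Always reporting the smaller p-value of the two gave 7.9%, 7.3%, 7.0% and 6.4% at ρ = 0.3, 0.5, 0.7 and 0.9. With skewed data (lognormal, log SD 1, 0% to 50% zeros) the same rule gave about 3% to 6%, because each test alone is conservative there.

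**4. Skewed MME.** Zeros are plausible: besides adult age, the only inclusion criterion is being "Referred for chronic pain OT" at the named centres, and opioid use is not required. Power was simulated with the skewed data above and an assumed 50% reduction in MME.

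- 50% zeros, ρ = 0.3: raw-scale ANCOVA about 7%, Mann-Whitney about 10%.
- No zeros: raw ANCOVA 20% to 63% and Mann-Whitney 16% to 59% across ρ.
- Rank ANCOVA beat raw ANCOVA in every skewed setting (for example 31% against 20% with no zeros) and matched or beat Mann-Whitney within simulation error.

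**5. More covariates.** If k covariates explain nothing beyond baseline MME, the interval relative to baseline MME alone is √[16/(17 − k)] × t(18 − k)/t(17). This is 1.080 for k = 3 (adding age and gender), and 1.182 and 1.245 for k = 5 and 6 (adding two or three PROMIS scores as well).

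**The case against.** The strongest reply is that the plan has a workable default: covariate-free tests under the primary heading and regression under the secondary one. On that reading the unadjusted test leads, it is valid, and one sentence would confirm it. Much of this stands. The sections do not contradict each other; what is missing is a statement of order. Declaring the unadjusted test primary would also close the choice, but would give up the precision in step 1.

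A second reply, that raw-scale ANCOVA is the wrong universal remedy, also stands. With many zeros it can do worse than the Mann-Whitney test the plan already names (step 4). A narrower interval than the change-score t-test is therefore not enough to recommend it for skewed MME.

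A third reply is that the error inflation is easily overstated. Adding a model with age and gender, and also the Mann-Whitney test, and always taking the best of four gives 8.2% to 9.7% with normal data. A reader might infer that the plan's error rate is near 10%. The documents do not support that. The figure mixes the adjustment question with the choice of test, which the plan links to non-normality at least for the within-group tests. Nothing suggests that the sponsor would always report the smallest p-value.

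The exploratory label in Challenges Due to Small Sample Size lowers the stakes, but it does not tell a reader which MME estimate is the primary result.

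**Conclusion.** The omission is certain from the text: the plan does not say whether the primary MME comparison is adjusted for baseline MME, or which result leads. Its size depends on assumed inputs. With normal data the forgone precision runs from about 17% of interval width at ρ = 0.3 to nothing near ρ = 0.87. The two-way choice adds at most about 3 percentage points of false positives with normal data (8% − 5%) and about 1 point with skewed data (6% − 5%).

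Two stronger readings fail. A reader might infer that the unadjusted comparison is biased; randomisation makes it valid, and chance imbalance is part of its sampling error. A reader might also infer that the plan ignores baseline MME; the covariate section lists it, but conditionally. Severity is low to modest given the exploratory label.

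**What to change.** 1. **Primary Analysis, MME.** State that the primary between-group analysis adjusts for baseline MME only. If MME is approximately normal, use ANCOVA of 8-week MME on arm and baseline MME. If it is not, use ANCOVA on ranks (ranked 8-week MME on arm and ranked baseline MME). Make the choice on data pooled across arms, before results by arm are seen. Fit the model in each imputed dataset and pool. Report the adjusted mean difference with 95% CI in either case.
2. **Sensitivity analysis, MME.** Keep the unadjusted t-test or Mann-Whitney test on change in this role, and say that it does not replace the primary result.
3. **PROMIS measures.** Keep the existing between-group tests and the baseline regression in Secondary Analysis, so that an MME-only edit does not remove the between-arm test for PROMIS.
4. **Adjustment for Covariates.** Limit the primary comparison to baseline MME. Put age, gender and named PROMIS scores in one supportive model.
5. **Time point.** Study Objectives still sets the primary objective at three months, while Statistical Considerations uses 8 weeks. Reconcile these so that the model has one outcome time.

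The cost is SAP wording and a few lines of R, with no new data. Statistically it costs one degree of freedom, an interval about 1% wider if ρ is near 0.9, and, in the rank version, a p-value that does not correspond directly to the reported mean difference. The documents do not say whether results by arm have been seen. Call the analysis pre-specified only if it is fixed before then; otherwise report both results and say when the change was made.
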